6.2. Informed Consent

All participants (or their legally authorized representatives) will provide written informed consent using an IRB-approved form detailing the study's purpose, duration, procedures, risks, benefits, and privacy protections. Informed consent allows the study team to access participant medical records, collect survey and PRO data, and link external datasets (e.g., claims, mortality, genetic testing) for approved research purposes. Participants will have the opportunity to ask questions prior to signing and will receive a copy of the signed consent for their records. Consent can be withdrawn at any time without penalty. Consent materials will be available electronically, with printable copies provided via the MPN Research Foundation website. A secure, encrypted system will capture and store electronic signatures.

6.3. Visit Schedule

The Registry is designed for extended longitudinal follow-up, with no required in-person study visits due to its non-interventional, observational nature. Data will be collected continuously through EMRs, PROs, insurance claims, mortality data, and linkages to affiliated registries.

The visit schedule aligns with structured follow-up intervals to ensure consistent longitudinal tracking of disease progression, treatment response, and post-enrollment clinical markers. Retention and engagement strategies will be employed to maintain data completeness and minimize loss to follow-up.

6.3.1. Data Collection Intervals and Structured Follow-Up Schedule

Participants will be followed for a minimum of five years, with many continuing beyond ten years.

| Follow-Up | Data Collected | Collection Method |
|-----------|----------------|-------------------|
|-----------|----------------|-------------------|

| Timepoint | | |
|----------------------------|---|---|
| Baseline (Enrollment) | Demographics, medical history, WHO 2022 MPN subtype, other hematologic disease information (e.g., post-MPN AML, MDS/MPN overlap syndrome as defined above, history of SCT and/or BMT) baseline labs, molecular testing (if available), treatment history, and PROs (MPN-SAF TSS, EORTC QLQ-C30, modified PHQ-9, PGI-S, PROMIS Short Form v1.0 – Fatigue 8a) | Initial EMR extraction, PROs, insurance claims |
| Every 3 Months (0-10+ yrs) | Symptom burden updates (MPN-SAF TSS + PGI-S) | PROs |
| Every 6 Months (0-10+ yrs) | Updates on disease status, treatment changes, adverse events, healthcare utilization, molecular/genetics results (if available), mortality status, progression milestones, and PROs (MPN-SAF TSS, EORTC QLQ-C30, modified PHQ-9, PROMIS Short Form v1.0 – Fatigue 8a) | EMR reauthorization, PROs, claims retrieval, mortality data linkage |

6.3.2. Disease Progression and Post-Enrollment Markers

The Registry will monitor disease evolution, therapeutic response, and emerging clinical risks through ongoing data collection from EMRs, laboratory results, imaging reports, mortality linkages, healthcare utilization data, and PROs.

Key post-enrollment markers include:

- **Molecular and Genetic Changes:** Emergence of high-risk mutations and shifts in VAF over time.
- **Bone Marrow and Imaging Biomarkers:** Assessments of fibrosis and splenomegaly progression, based on clinically indicated bone marrow biopsies or imaging.
- **Symptom Burden and Quality of Life:** Trends captured through validated PROs, including MPN-SAF TSS, EORTC QLQ-C30, modified PHQ-9, PGI-S, and PROMIS Fatigue Short Form.
- **Cardiovascular and Thrombotic Events:** Documentation of new complications such as deep vein thrombosis, pulmonary embolism, stroke, or myocardial infarction.
- **Mortality Status:** Vital status and cause of death, obtained through national mortality data linkages.

To maintain complete and up-to-date records, participants will be asked every six months to refresh their EMR data access permissions.

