4. OBJECTIVES

4.1. Primary Objectives

Stage 1: Feasibility Phase

The study will begin with a 12- to 24-month feasibility phase focused on participant retention, data completeness, EMR integration, and engagement strategies. Results from this phase will help optimize study operations, guide participant engagement, and inform potential protocol amendments.

- Evaluate enrollment feasibility and participant characteristics during the first 12–24 months.
- Characterize participant demographics, geographic distribution, and clinical settings.
- Assess inclusion of underrepresented populations to enhance the generalizability and heterogeneity of RWD.
- Assess representativeness of enrolled participants relative to the broader U.S. MPN population, ensuring alignment with clinical and demographic patterns.
- Determine the proportion of participants providing a Minimal Viable Dataset (MVD) at enrollment.
- Monitor consent rates for longitudinal EMR access and secondary data use.
- Identify gaps in baseline data completeness and develop strategies to mitigate missing information.
- Track participant retention at 12, 18, 24, and 36 months, and evaluate completion of at least three consecutive follow-ups.
- Identify early indicators of dropout or disengagement to inform retention strategies.
- Monitor response rates to quarterly PRO surveys (e.g., MPN-SAF TSS, PROMIS Short Form v1.0 – Fatigue 8a) and evaluate follow-up strategies (automated vs. manual).
- Assess the proportion of participants using secondary contacts (caregivers, clinicians) for follow-up.
- Measure success rates of EMR integration across sites using FHIR-based interoperability, compare self-reported and EMR-extracted data, and validate processing scalability.

Stage 2: Surrogate Endpoint Phase

- Establish composite surrogate endpoints integrating genetic markers (e.g., variant allele frequency shifts), clinical indicators (e.g., fibrosis progression, cytopenias), inflammatory markers (e.g., cytokine levels), and PROs (e.g., MPN-SAF TSS, PROMIS trends).
- Ensure surrogate endpoints align with FDA and EMA regulatory standards for clinical trials.
- Incorporate RWD (EMR, claims, PROs) to validate surrogate markers of disease progression.
- Determine time from baseline to first progression event (e.g., ET → PV → MF, blast phase transformation) and assess median time to progression by subtype.
- Measure progression rates per WHO 2022/IWG-MRT criteria using updated risk stratification models.

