- Develop surrogate endpoints predictive of disease progression and treatment response to support drug development.
- Compare progression rates in treated vs. untreated cohorts and validate endpoints using external registries (e.g., SEER, NCDB, Mayo Clinic MPN Database, ELN).
- Monitor overall survival (OS) and progression-free survival (PFS), evaluating prognostic significance of surrogate endpoints for future trials.

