4.2. Secondary Objectives

- **Characterize Disease Burden and Risk Stratification**
Develop a composite risk model distinguishing high- and low-risk patients by integrating genetic, inflammatory, and clinical markers. Assess how cytokine levels and inflammatory pathways influence disease trajectory and symptom burden.
- **Evaluate Treatment Response as a Surrogate for Disease Progression**
Compare progression rates in patients treated with JAK inhibitors, interferons, investigational agents, and other drugs. Determine whether therapy-induced molecular or clinical changes correlate with improved outcomes.
- **Analyze Genetic and Morphological Disease Evolution**
Monitor available variant allele frequency (VAF) changes in high-risk mutations and evaluate bone marrow fibrosis progression, where data is available, to understand clinical implications.
- **Assess Quality of Life and Symptom Burden at Disease Progression**
Track longitudinal changes using validated PROs, including MPN-SAF TSS, EORTC QLQ-C30, modified PHQ-9, PGI-S, and PROMIS Short Form v1.0 – Fatigue 8a, to evaluate how symptom burden correlates with disease progression

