4.3. Exploratory Objectives

- **Develop Predictive Models for MPN Progression**
Train and validate artificial intelligence (AI) and machine learning (ML) models to predict time to disease progression, likelihood of transformation to accelerated or blast phase, and overall survival using early clinical and molecular indicators.
- **Validate Findings Across External Data Sources**
Compare registry data against European MPN registries, Mayo Clinic datasets, and claims-based registries to assess consistency, generalizability, and cross-cohort validation.
- **Assess Healthcare Utilization and Economic Impact**
Track hospitalization rates, transfusion needs, major interventions, and conduct cost-effectiveness analyses to inform early intervention strategies and support health policy development
- **Assess Early Patterns of Care and Treatment Setting Influence**
Evaluate how early patterns in healthcare utilization—including differences between academic centers, community hospitals, and rural clinics—impact disease monitoring, treatment choices, referral patterns, and long-term outcomes. Identify disparities in access to specialized care and examine how practice setting influences adherence to evidence-based guidelines and clinical outcomes.

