9.9 Consideration for Potential Data Biases

This study is an observational, non-interventional registry that relies on data collected from multiple sources, including EMRs, PROs, validated survey instruments, and claims data. Such a study design is inherently associated with data biases, including misclassification, recall bias, and missing data, which cannot always be independently verified by investigators.

However, the large sample size, objective disease assessments, and multi-source data validation minimize these limitations. To further enhance data reliability, the Registry will implement a structured quality control framework in collaboration with the data vendor. This framework includes:

- Automated Data Validation Checks – Incoming data will be systematically screened for missing values, internal inconsistencies, and entry errors using predefined validation rules aligned with ICD-10, SNOMED CT, and LOINC terminologies.

- Cross-Source Data Verification – Self-reported patient data will be cross-checked with EMR-derived records, laboratory values, and claims data to ensure consistency and flag discrepancies requiring manual review.
- Longitudinal Data Quality Monitoring – The completeness and accuracy of collected data will be reviewed at predefined study milestones (e.g., 6 months, 12 months, 18 months, annually) to detect unexpected deviations that may indicate systematic errors or reporting inconsistencies.
- Audit Trails and Data Traceability – All modifications to the dataset, including data corrections, updates, and deletions, will be logged through an automated audit trail system to ensure full traceability and compliance with research standards.
- Outlier Detection and Resolution – Advanced statistical methods and machine learning algorithms will be used to flag outlier data points that significantly deviate from expected clinical patterns. Flagged data will undergo secondary review before inclusion in analyses.
- Investigator-Led Quality Assurance Reviews – The PI and designated data management personnel will conduct periodic reviews to assess adherence to protocol-defined data quality standards, document findings, and implement corrective actions.

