10.5. IWG-MRT Criteria for Secondary Myelofibrosis

| Criteria for post-polycythemia vera myelofibrosis | |
|---|--|
| Required criteria: | |
| 1 | Documentation of a previous diagnosis of polycythemia vera as defined by the WHO criteria |
| 2 | Bone marrow fibrosis grade 2–3 (on 0–3 scale) or grade 3–4 (on 0–4 scale), ^a |
| Additional criteria (two are required): | |
| 1 | Anemia ^b or sustained loss of requirement of either phlebotomy (in the absence of cytoreductive therapy) or cytoreductive treatment for erythrocytosis |
| 2 | A leukoerythroblastic peripheral blood picture |
| 3 | Increasing splenomegaly defined as either an increase in palpable splenomegaly of ≥ 5 cm (distance of the tip of the spleen from the left costal margin) or the appearance of a newly palpable splenomegaly |
| 4 | Development of ≥ 1 of three constitutional symptoms: $>10\%$ weight loss in 6 months, night sweats, unexplained fever ($>37.5^{\circ}\text{C}$) |
| Criteria for post-essential thrombocythemia myelofibrosis | |
| Required criteria: | |
| 1 | Documentation of a previous diagnosis of essential thrombocythemia as defined by the WHO criteria |
| 2 | Bone marrow fibrosis grade 2–3 (on 0–3 scale) or grade 3–4 (on 0–4 scale), ^a |
| Additional criteria (two are required): | |
| 1 | Anemia ^b and a ≥ 2 mg ml $^{-1}$ decrease from baseline hemoglobin level |
| 2 | A leukoerythroblastic peripheral blood picture |
| 3 | Increasing splenomegaly defined as either an increase in palpable splenomegaly of ≥ 5 cm (distance of the tip of the spleen from the left costal margin) or the appearance of a newly palpable splenomegaly |
| 4 | Increased LDH (above reference level) |
| 5 | Development of ≥ 1 of three constitutional symptoms: $>10\%$ weight loss in 6 months, night sweats, unexplained fever ($>37.5^{\circ}\text{C}$) |

Abbreviations: IWG-MRT, International Working Group for Myelofibrosis Research and Treatment; LDH, lactate dehydrogenase; post-ET MF, post-essential thrombocythemia myelofibrosis; post-PV MF, post-polycythemia vera myelofibrosis.

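### Secondary myelofibrosis counts only if a marrow is taken, and marrows are taken only when care calls for them, so treatment comparisons of progression partly reflect biopsy frequency wherever that frequency differs

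*Protocol*

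**What the plan says.** - **Criteria.** Protocol Section 4.1, Stage 2: "Measure progression rates per WHO 2022/IWG-MRT criteria using updated risk stratification models". For both post-PV and post-ET MF, Appendix 10.5 lists as required "Bone marrow fibrosis grade 2–3 (on 0–3 scale) or grade 3–4 (on 0–4 scale"), together with two additional criteria.
- **Ascertainment.** Section 6.3.2: "Assessments of fibrosis and splenomegaly progression, based on clinically indicated bone marrow biopsies or imaging". Section 6.3 has "no required in-person study visits due to its non-interventional, observational nature", and Section 4.2 will "evaluate bone marrow fibrosis progression, where data is available".
- **Endpoint and analysis.** Section 9.1 makes time to documented progression a primary endpoint, with Kaplan-Meier and Cox methods. Section 4.1 also counts ET to PV and blast transformation as progression events.
- **Comparisons.** Section 4.1: "Compare progression rates in treated vs. untreated cohorts and validate endpoints using external registries". Section 4.2 compares progression rates between JAK inhibitors, interferons, investigational agents and other drugs.
- **Safeguards.** Section 9.7 uses propensity scores against confounding and selection. Section 9.9 names misclassification, recall bias and missing data, then says that "the large sample size, objective disease assessments, and multi-source data validation minimize these limitations".

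**The concern.** A patient whose marrow has become fibrotic but who has not been biopsied cannot be counted as having post-PV or post-ET MF, whatever the other signs show. When a biopsy is done, the event is dated to the biopsy and not to the onset of fibrosis. The intensity of care therefore helps to decide whether and when the event is seen, and treatment, which is part of care, is the exposure being compared. A group that is biopsied more often would show more and earlier progression at the same true rate. The error could favour either side of a comparison.

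The listed safeguards do not reach this. Propensity scores balance factors measured before or at the start of treatment, not how often the outcome is looked for afterwards. A cross-source check cannot recover a biopsy that was never done. A larger sample leaves a systematic difference as it is and makes it more likely to reach significance.

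**Working it through.** **1. The plan's own figure.** Table 1 (80% power, 5% type I error, 50% progression) is reproduced by HR = exp[(1.960 + 0.842)/√(0.5·N·p(1−p))], with p the marker prevalence. At p = 50%, N = 1000 gives 1.285 (stated 1.3) and N = 2000 gives 1.194 (stated 1.2). All 16 cells agree within 0.015, and none is disputed here. At the planned N of about 1500 and p = 50%, the same formula gives 1.227, or about 1.23. This is the smallest effect that the registry is sized to detect in its most favourable case.

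**2. Documented versus true progression.** The protocol gives no biopsy rates, so the rates and delays here are assumptions. Let onset be exponential with rate l, the same in both groups (true ratio 1). Let the delay from onset to biopsy be exponential with mean 1/m. Then

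P(documented by T) = 1 − [m·exp(−lT) − l·exp(−mT)]/(m − l).

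With l = 0.04 per year and T = 5 years (the minimum follow-up in Section 6.1), true progression is 1 − exp(−0.2) = 18.1%. If half the events need a marrow, documented progression is the average of the true figure and the delayed figure.

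| Mean delay | All events need a marrow | Half need a marrow |
|---|---|---|
| 0.5 years | 16.5% | (18.13 + 16.46)/2 = 17.3% |
| 2 years | 11.7% | (18.13 + 11.72)/2 = 14.9% |
| 6 years | 6.0% | (18.13 + 6.00)/2 = 12.1% |

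Ratios of documented progression:

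| Delays compared | All, 5 years | Half, 5 years | All, 10 years | Half, 10 years |
|---|---|---|---|---|
| 0.5 vs 2 years | 1.40 | 1.16 | 1.16 | 1.07 |
| 2 vs 6 years | 1.95 | 1.24 | 1.53 | 1.19 |

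With true rates from 2% to 8% per year, the 5-year ratios when all events need a marrow are 1.39–1.41 and 1.94–1.96.

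**3. The same effect in a Cox model.** This simulation used a true HR of 1, censoring at 5 years, and an exponential wait to the next biopsy with a different mean in each group. The false-positive rate is for 1500 patients split equally, at a nominal 5%.

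| True 5-year progression | Mean wait (years) | HR, all need a marrow | False positives | HR, half need a marrow | False positives |
|---|---|---|---|---|---|
| 50% | 1 vs 2 | 1.35 | 94% | 1.13 | 40% |
| 50% | 1 vs 3 | 1.70 | 100% | 1.26 | 82% |
| 50% | 2 vs 4 | 1.58 | 99.8% | 1.18 | 53% |
| 20% | 1 vs 2 | 1.30 | 47% | 1.13 | 13% |
| 20% | 1 vs 3 | 1.61 | 90% | 1.20 | 33% |
| 20% | 2 vs 4 | 1.52 | 73% | 1.16 | 18% |

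With equal waits (2 vs 2) the HR is 1.00–1.01 and the false-positive rate is 4.6–6.0%. Under Table 1's 50% progression, the artefact exceeds 1.23 in all three cases when every event needs a marrow, and in one of three when half do.

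**The case against.** **Not all progression needs a marrow grade.** A reader might infer that without a biopsy there is no progression event at all. The documents do not support that. Section 4.1 also counts blast transformation and ET to PV, and Section 5.1 admits patients who already have MF, accelerated or blast phase disease, or a transplant, for whom Appendix 10.5 does not define the next event. This stands, and it is why the half-share columns matter.

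**The care-setting objective does not name progression rates.** It is tempting to extend the point to Section 4.3, which looks at care patterns "including differences between academic centers, community hospitals, and rural clinics". That objective concerns monitoring, treatment choices, referral and long-term outcomes, and unequal monitoring is itself one of its subjects. The point reaches it only if progression is used as the outcome there.

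**Unequal biopsy rates are not shown.** The protocol gives none, so the bias is conditional. The additional criteria in Appendix 10.5, such as anemia or spleen growth, could themselves prompt a biopsy and shorten the delay in both groups. A mean delay of 6 years exceeds the 5-year minimum follow-up, and follow-up beyond ten years shrinks the ratios. All of this limits the size and leaves the mechanism in place.

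**Clinically indicated biopsy is no defect in a non-interventional registry.** Agreed. The protocol discloses the limit and names misclassification and missing data. What is wrong is the claim that sample size minimizes them.

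**Analysis detail belongs in the SAP.** That is largely fair: the SAP is not at hand and may cover interval censoring or biopsy rates. But the protocol itself fixes the endpoint, its ascertainment, the treatment comparisons and the assurance in Section 9.9. Overall survival is already a primary endpoint, which supplies part of the remedy.

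**Conclusion.** The point holds in conditional form, for post-PV and post-ET MF. Where biopsy frequency differs between treated and untreated patients or between drug classes, the compared rates of documented progression will partly reflect it. Under the assumed delays, with no true difference, the 5-year ratio is 1.40 to 1.95 if every event needs a marrow and about 1.16 to 1.24 if half do. It is smaller with longer follow-up. The half-share figures are the fairer guide to the composite, although the protocol does not give the true share. The figures also assume that the biopsy delay is unrelated to clinical signs. They show what could happen and do not estimate the bias in this registry.

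Section 9.9 is wrong to list large sample size as a protection. It is incomplete on objective assessments, because reading a marrow objectively does not make the timing of the biopsy objective. The protocol should be changed on this point, at modest cost.

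**What to change.** 1. **Section 6.3.2:** capture the date and result of every marrow in the EMR, including those without progression. Report biopsies per person-year by comparison group beside each treatment comparison of progression.
2. **Section 9.1:** report alongside each such comparison a companion endpoint that needs no fibrosis grade, namely blast transformation or death. Mortality linkage is already planned.
3. **Sensitivity analysis:** treat fibrotic progression as interval-censored between the last marrow without and the first marrow with grade 2–3 fibrosis (0–3 scale). Reconcile this with Section 7.2, which strips dates down to the year, for example by having the Honest Broker supply time intervals in place of dates.
4. **Section 9.9:** delete large sample size as a reason for low bias. Qualify the statement on objective assessments by noting that clinical care sets their timing. Name unequal outcome ascertainment as a limitation.
5. Apply items 1–3 to care-setting analyses only if progression is the outcome there.

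The cost is protocol and SAP wording plus added extraction and analysis of marrow records. No extra biopsies are needed and clinical care does not change. The companion endpoint will have fewer events, interval-censored estimates will be less precise, and finer time information must pass through the de-identification step.

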6.3.3. Patient Retention and Engagement Strategies

To support long-term participant retention, the Registry will implement a multi-faceted engagement approach that includes:

- **Automated Communications:**
Email and SMS reminders will notify participants about upcoming surveys, EMR data refreshes, and study milestones.
- **Aggregate Study Updates:**
Participants will periodically receive summaries of registry progress, including enrollment trends, geographic representation, heterogeneity metrics, and de-identified PRO findings (MPN-SAF TSS, EORTC QLQ-C30, modified PHQ-9, PGI-S, PROMIS Fatigue Short Form), delivered via secure channels.
- **Educational Materials:**
Plain-language resources will explain how participant contributions advance MPN research and improve understanding of disease progression.
- **Interactive Opportunities:**
Invitations to webinars, virtual town halls, or Q&A sessions will allow participants to hear updates directly from investigators.
- **Non-Monetary Incentives:**
Digital badges, certificates, or eligibility for future research opportunities will help sustain engagement.
- **Patient Support Access:**
A dedicated patient navigator will assist with survey completion, consent renewals, and EMR data access questions.

As PRO surveys and EMR refreshes occur approximately every six months, communications will reflect cumulative study updates. All outreach will use de-identified data, and participants will have secure access to their own summaries through the registry dashboard.

